#### 10.3.2. Change from Baseline in Mean HAQ Pain Score

The HAQ pain score will be administered at the Screening; prior to pegloticase infusion at the Day 1 and Weeks 6, 14, and 20 Visits during the Pegloticase Treatment Period; and at the End of Pegloticase Infusions Visit (if applicable), Week 24/End of Study/Early Termination and 3 month Post Treatment Follow-up Visits.

The HAQ pain score consists of a doubly anchored, horizontal visual analog scale (VAS) 15 cm in length, that is scored from 0 (no pain) to 100 (severe pain). Subjects are asked to rate the severity of the pain they have had because of illness in the past week by placing a vertical mark on the VAS. In order to convert the score to a 0-100 scale, the results (in cm) in the database will be divided by 15 then multiplied by 100.

Observed values and change from baseline in mean HAQ pain score will be summarized for each visit using descriptive statistics and 95% normal theory-based two-sided confidence interval by pegloticase treatment status (On Treatment and Overall).

#### 10.3.3. Change from Baseline in Mean HAQ-DI Score

The HAQ-DI score will be administered at the Screening visit; prior to pegloticase infusion at the Day 1 and Weeks 6, 14, and 20 Visits during the Pegloticase Treatment Period; and at the End of Pegloticase Infusions Visit (if applicable), Week 24/End of Study/Early Termination and 3 month Post Treatment Follow-up Visits.

The HAQ-DI is a self-report functional status instrument that can be filled out by a subject in less than 5 minutes and requires 1 minute to score. The index measures disability over the past week by asking a total of 20 questions covering 8 domains of function: dressing and grooming, arising, eating, walking, hygiene, reach, grip, and usual activities. There are at least 2 questions in each domain and the 8 domains represent a comprehensive set of functional activities. The HAQ-DI is calculated by scoring the answer to each question in the HAQ from 0 to 3, with 0 representing the ability to do without any difficulty, and 3 representing inability to do. Any activity that requires assistance from another individual or requires the use of an assistive device raises a 0 or 1 score to a 2. The highest score for each of the 8 domains is summed (range from 0 to 24) and divided by 8 to yield, on a scale with 25 possible values, a Functional Disability Index with a range from 0 to 3.

If a domain has all responses missing (including aids/devices) then the domain is considered missing. If some of the questions have a result and/or the aids/devices is checked, then use available values to calculate a domain score. The disability index is based on the number of domains answered and is computed only if the subject completes answers to at least 6 domains [Bruce and Fries, 2003]. That is, if 6 domains are non-missing, then the average of the 6 available scores will determine the Functional Disability Index. If < 6 domains are non-missing then the HAQ-DI score will be missing.

This document is confidential.

If “Other” option is checked in either of the “AIDS AND DEVICES” sections of the questionnaire, the corresponding “Other, Specify” field will be reviewed and categorized by Horizon Therapeutics into an appropriate domain of function, so it can be incorporated into the score.

Observed values and change from baseline in mean HAQ-DI score will be summarized for each scheduled visit using descriptive statistics and 95% normal theory-based two-sided confidence interval by pegloticase treatment status (On Treatment and Overall).

**10.4.** [Redacted]

10.4.1. [Redacted]

[Redacted]

[Redacted]

[Redacted]

[Redacted]

10.4.2. [Redacted]

[Redacted]

[Redacted]

[Redacted]	[Redacted]	[Redacted]	[Redacted]
[Redacted]	[Redacted]	[Redacted]	[Redacted]

This document is confidential.

10.4.3. [Redacted]

[Redacted]

10.4.4. [Redacted]

[Redacted]

[Redacted]

[Redacted]

[Redacted]

10.4.6. [Redacted]

[Redacted]

[Redacted]

- | [Redacted]
- | [Redacted]
- | [Redacted]
- | [Redacted]
- | [Redacted]
- | [Redacted]

This document is confidential.

[Redacted]

- | [Redacted]
- | [Redacted]
- | [Redacted]
- | [Redacted]
- | [Redacted]

[Redacted]

If any single tophus shows progression, or if a new tophus appears during the study (as identified on the

[Redacted]

[Redacted]

[Redacted]

[Redacted]

- | [Redacted]
  - | [Redacted]
  - | [Redacted]
  - | [Redacted]

[Redacted]

[Redacted]	[Redacted]
[Redacted]	[Redacted]

This document is confidential.

[REDACTED]	[REDACTED]
[REDACTED]	[REDACTED]
[REDACTED]	[REDACTED]
[REDACTED]	[REDACTED]

[REDACTED]

[REDACTED]

[REDACTED]

[REDACTED]

[REDACTED]

10.4.7. [REDACTED]

[REDACTED]

[REDACTED]

[REDACTED]

10.4.8. [REDACTED]

[REDACTED]

This document is confidential.

[REDACTED]

[REDACTED]

[REDACTED]

[REDACTED]

[REDACTED]

MAP will be calculated from SBP and DBP as  $MAP = 1/3 * SBP + 2/3 * DBP$ .

Observed values and mean change from baseline in SBP, DBP and MAP at each visit will be summarized using descriptive statistics and 95% normal theory-based two-sided confidence interval. Line plots by visit for mean SBP, mean DBP, mean CFB (change from baseline) in SBP, and mean CFB (change from baseline) in DBP will be provided.

10.4.10. [REDACTED]

[REDACTED]

[REDACTED]

10.4.11. [REDACTED]

[REDACTED]

This document is confidential.

[REDACTED]

[REDACTED]

[REDACTED]

[REDACTED]

10.4.12. [REDACTED]

[REDACTED]

10.4.13. [REDACTED]

[REDACTED]

10.4.14. [REDACTED]

[REDACTED]

[REDACTED]

[REDACTED]

10.4.15. [REDACTED]

[REDACTED]

This document is confidential.

[Redacted]

[Redacted]

This document is confidential.

[Redacted]

## 11. Pharmacokinetics and Anti-drug Antibody Analysis

Serum samples for PK analysis of pegloticase will be collected after the end of infusion on Day 1 (prior to discharge); prior to the pegloticase infusion and after the end of the infusion (prior to discharge) at Weeks 2, 6, 14, and 22. Additional PK samples will be collected at the Week 21 Visit, the End of Pegloticase Infusions Visit (if applicable), and the Week 24/End of Study/Early Termination Visit.

Concentrations for pegloticase will be summarized using descriptive statistics by scheduled timepoint for the PK population.

The following presentations of subject serum pegloticase concentration data covered in this SAP will be provided:

- A listing including subject, week/time point (actual, planned), treatment and serum concentrations. End of infusion sampling times are expressed relative to the start time of infusion.
- A table summary of serum pegloticase concentrations at each time point (n; mean, SD, coefficient of variation (CV)% calculated as  $100\% \times SD/mean$ , minimum, 25th percentile, median, 75th percentile and maximum) for the PK Population.

Concentrations below the limit of quantification (BLQ) collected on Day 1 pre-dose will be summarized as zero. All other concentrations BLQ will be excluded from the analysis summaries.

Serum samples for evaluation of anti-PEG and anti-uricase IgG antibodies will be collected prior to the pegloticase infusion on Day 1 and at the Week 2, 6, 14, 22 Visits, the End of Pegloticase Infusions Visit (if applicable), the Week 24/End of Study/Early Termination Visit, and the 3 month Post Treatment Follow-up Visit. In the event of an AE suspected to be an infusion reaction, a serum sample will be collected in a serum separating tube at that time or at the subsequent visit for future evaluation of pegloticase antibodies.

Using the ITT Population for anti-PEG IgG antibodies, the number and percentage of subjects with ADA positive at baseline, ADA negative at baseline, ADA positive at post-baseline but negative at baseline or with increase in titer from baseline, ADA positive at post-baseline but negative at baseline, subjects with increase in titer from baseline who were ADA positive at baseline, and ADA negative or subjects with no increase in titer from baseline will be summarized by scheduled timepoint. Similarly for anti-uricase IgG antibodies, the number and percentage of subjects with ADA positive at baseline and post-baseline will be summarized by scheduled timepoint.

Kaplan-Meier estimates of the time to positive anti-PEG, and positive anti-uricase with 25th percentile, median, 75th percentile, and 95% CI, along with a Kaplan-Meier curve will be produced. Further, the mean and coefficient of variation (CV%) of antibody titers (for samples confirmed positive) will be provided by visit and time point.

Further, the mean and CV% of pegloticase concentrations will be provided by visit in the subset of subjects who are ADA positive (defined as positive for anti-PEG or anti-uricase antibodies) and ADA negative (defined as negative for both anti-PEG and anti-uricase antibodies) for each visit. This analysis will be provided for the ITT Population.

This document is confidential.

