16. For all subjects, serum samples for pegloticase PK analysis will be collected approximately 15 minutes to 2 hours after the end of infusion on Day 1; prior to infusion and approximately 15 minutes to 2 hours after the end of the infusion at Weeks 2, 6, 14, and 22. An additional PK sample will be collected at Week 21, the End-of-Pegloticase-Infusions Visit (if applicable) and the Week 24/End-of-Study/Early Termination Visit.
17. Serum samples for measurement of sUA levels will be collected at the Screening Visit, within 48 hours prior to each pegloticase infusion and after the end of each pegloticase infusion prior to discharge from the site. Additional serum samples for sUA levels will be collected at non-infusion Visits at Weeks 21 and 23 and the End-of-Pegloticase-Infusions Visit (if applicable), the Week 24/End-of-Study/Early Termination Visit, and the 3-month Follow-up Visit. For subjects whose previous visit's pre-infusion sUA value is > 6 mg/dL, two separate samples/tubes of blood should be collected within 48 hours prior to the pegloticase infusion (except on Day 1 when only 1 pre-infusion sample is required for the central laboratory); one sample/tube will be assessed by the site's local laboratory for pre-infusion sUA results for on-study subject management. If a local laboratory sample is drawn (within 48 hours prior to the pegloticase infusion), a sample for the central laboratory will be drawn prior to the pegloticase infusion on the day of the visit. The second sample/tube will be sent to the central laboratory for analysis and recording in the database. Hand held uric acid measurement devices may be provided to measure subject uric acid levels in real time. If hand held devices are provided, blood uric acid levels prior to each pegloticase infusion and after the end of each pegloticase infusion prior to discharge from the site at the selected visits will be recorded in database, but NOT to be used to manage pegloticase treatment. See the Laboratory Manual for instructions for alternate scenarios.

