##### **9.3.3.1.1 Study considerations for subjects ending pegloticase infusions prior to 24 weeks**

- All subjects will remain on study through Week 24 regardless of whether they stop infusions due to sUA stopping rules or other reason (e.g., withdrawal of consent for pegloticase infusions).
- Subjects are encouraged to continue to participate in all visits through the end of the study. Subjects are especially encouraged to complete study visits at the study site during key efficacy and safety collections at Weeks 20, 21, 22, 23, and 24 so that sUA labs and other key assessments can be completed. During visits between these key efficacy and safety collection visits, in subjects who have stopped infusions, subjects may complete study visits

in person or via telephone to collect AEs, concomitant medications and gout flare information.

- Activities related to pre/post infusion monitoring or medication dispensation will not be completed once a subject has stopped pegloticase infusions. These activities include:
  - Infusion reaction prophylaxis;
  - IR prophylaxis compliance;
  - Pegloticase infusion; and
  - Pegloticase PK sampling
- Re-introduction of oral ULTs should not start until after the End of Pegloticase Visit laboratory tests are collected.

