### **6.3. Pharmacokinetic Population**

The Pharmacokinetic population (PK) will include all subjects who receive at least 1 dose of pegloticase and have a post-pegloticase sample evaluable for PK analysis.

This document is confidential.

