**Table 5: Visit Windows for Assigning End of Study/ET and End of Pegloticase Visits to a Scheduled Visit (PK Assessments)**

Study Period	Visit	Target Day a	Window for Reassignment to Scheduled Visit (days)
Pegloticase Treatment	Day 1	1	1
	Week 2	15	2 – 29
	Week 6	43	30 – 71
	Week 14	99	72 – 124
	Week 21	148	125 – 152
	Week 22	155	153 – 162
	Week 24	169	≥163

a Study days in the Pegloticase Treatment Period will be calculated relative to the first dose of Pegloticase.

**Table 6: Visit Windows for Assigning End of Study/ET and End of Pegloticase Visits to a Scheduled Visit (Blood and Urine Collection for Allantoin)**

Study Period	Visit	Target Day a	Window for Reassignment to Scheduled Visit (days)
Pegloticase Treatment	Day 1	1	1
	Week 2	15	2 – 22
	Week 4	29	23 – 36
	Week 6	43	37 – 50
	Week 8	57	51 – 64

This document is confidential.

Study Period	Visit	Target Day a	Window for Reassignment to Scheduled Visit (days)
	Week 10	71	65 – 85
	Week 14	99	86 – 113
	Week 18	127	114 – 141
	Week 22	155	142 – 162
	Week 24	169	≥163

a Study days in the Pegloticase Treatment Period will be calculated relative to the first dose of Pegloticase.

In the event that an End of Study/ET or End of Pegloticase visit is reassigned to a visit for which the subject has scheduled data collected, the data from the nominal scheduled visit will take precedence and the data from the End of Study/ET or End of Pegloticase visit will not be summarized. If the End of Study/ET or End of Pegloticase visit maps to a visit where the assessment was scheduled to be collected, and a scheduled collection is not available at that time point, the End of Study/ET or End of Pegloticase visit data will be summarized in the scheduled visit assessment.

For visit summaries and changes from baseline summaries, ET and End of Pegloticase visits will also be summarized separately, in addition to the visit to which it was windowed, for summaries by visit.

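### SAP 11 pools pegloticase concentrations without regard to whether the subject is still being dosed, and Table 5 can place a 14-day sample in the 7-day Week 21 cell

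*SAP*

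**What the plan says.** **Summaries.** SAP 11 gives the main PK rule: "Concentrations for pegloticase will be summarized using descriptive statistics by scheduled timepoint for the PK population". Under SAP 6.3 a subject belongs to that population after one dose if they "have a post-pegloticase sample evaluable for PK analysis"; being on drug at the visit is not required. SAP 11 adds that "the mean and CV% of pegloticase concentrations will be provided by visit in the subset of subjects who are ADA positive", with a matching summary for ADA-negative subjects. No pre- or post-infusion time point is named there, although both are drawn at Weeks 2, 6, 14 and 22. On values below the limit of quantification (BLQ) after the Day 1 pre-dose sample, SAP 11 says: "All other concentrations BLQ will be excluded from the analysis summaries".

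**Treatment status.** SAP 10.3 (secondary efficacy), 12.4 (laboratory) and 12.6 (vital signs other than blood pressure) define or use a split by treatment status. SAP 11 does not.

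**Sampling after stopping.** Protocol 9.3.3.1.1 says "Activities related to pre/post infusion monitoring or medication dispensation will not be completed once a subject has stopped pegloticase infusions", and its list names PK sampling. Protocol 9.1 and SAP 4.1 say the opposite: later visits run in full, apart from the infusion and its premedication. Footnote 16 of Protocol 2.1 says "An additional PK sample will be collected at Week 21, the End-of-Pegloticase-Infusions Visit (if applicable) and the Week 24/End-of-Study/Early Termination Visit", with no exception for subjects off drug. Protocol 9.5.7.3 and 9.5.7.4 list PK at the End-of-Pegloticase and Week 24 visits.

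**Windowing.** SAP Table 5 assigns PK by study day: Week 14 is Days 72 to 124, Week 21 is 125 to 152, Week 22 is 153 to 162. Where the scheduled cell is empty, "the End of Study/ET or End of Pegloticase visit data will be summarized in the scheduled visit assessment". A nominal sample takes precedence if there is one.

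**The concern.** Drug concentration depends on dosing more directly than any other variable in the study, yet it is one that the SAP does not separate by dosing status. Subjects who stop infusions are meant to stay to Week 24, so their samples can enter the same cells as those of subjects still being dosed.

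The ADA split is the more exposed table. Protocol 7.1.2 reports that 2% of subjects with high antibody titers kept their urate response, against 63% of those without. Loss of response triggers the stopping rule, so ADA status and dosing status are likely to move together. A reader of the table could not tell faster clearance from stopped dosing.

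**Working it through.** The plan gives no PK figure to reproduce. Inputs from the documents are the visit days (SAP Table 1: Week 16 = Day 113, Week 18 = 127, Week 20 = 141, Week 21 = 148, Week 22 = 155), the Table 5 windows and the End-of-Pegloticase timing (within 2 weeks of the last infusion). For scale, 14 of 20 responders leaves 6 possibly off drug, and 43.5% leaves 20 × (1 − 0.435) = 11.3. This treats non-response as being off drug, which is an assumption. Half-life h and the quantification limit (LLOQ) are not in the public text. I assume first-order decay, h of 7 to 21 days, and an LLOQ of 2% to 30% of an on-drug 14-day trough.

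**1. What Week 21 is meant to be.** 148 − 141 = 7 days post-dose. It is the only planned mid-interval sample.

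**2. If sampling stops after the End-of-Pegloticase visit.**
- Last infusion Week 16: 113 + 14 = Day 127. Last infusion Week 18: 127 + 14 = Day 141. Both lie in 125 to 152, and the Week 21 cell is otherwise empty, so the sample fills it.
- For the Week 16 stopper this needs a visit at least 125 − 113 = 12 days post-dose. For the Week 18 stopper any day in the two weeks qualifies.
- A 14-day value relative to a 7-day value is 0.5^(7/h): 0.50 at h = 7, 0.71 at h = 14.
- With 14 correct values set to 1 and one misplaced value, the mean is (14 + 0.50)/15 = 0.967 or (14 + 0.71)/15 = 0.981, which is 3.3% or 1.9% low.

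**3. If sampling continues.**
- The nominal Week 21 sample takes precedence. For the same two subjects it is drawn 148 − 113 = 35 or 148 − 127 = 21 days post-dose.
- At Week 22 pre-infusion, a subject last infused at Week 18 is 155 − 127 = 28 days post-dose, 14 days past a trough. The residual r = 0.5^(14/h) is 0.25, 0.50 or 0.63 of a trough at h = 7, 14 or 21.
- One such subject among 15: (14 + r)/15 = 0.95, 0.967 or 0.975.
- All 6 off-drug subjects last infused at Week 18: (14 + 6r)/20 = 0.78, 0.85 or 0.89. All 11: (9 + 11r)/20 = 0.59, 0.73 or 0.80. These are deliberately extreme: same stopping week, all sampled, all measurable. At h = 7 with an LLOQ of 30% of trough, the residual is BLQ and the mean stays 1.00.

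**4. Long-stopped subjects.** Last infusion Week 6 (Day 43), sampled at Week 24 (Day 169): 126 days, or 112 past a trough. The residual is 0.5^(112/14) = 0.4% at h = 14 and less at h = 7, below every assumed LLOQ. SAP 11 drops it and the mean stays 1.00. Only at h = 21 with an LLOQ of 2% would it be counted: 0.5^(112/21) = 2.5%, and with 6 such subjects (14 + 6 × 0.025)/20 = 0.71.

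**5. Time point.** An End-of-Pegloticase sample after a last infusion at Week 10 or 12 falls near Day 85 or 99 and maps to Week 14. It is a 14-day value, comparable with the pre-infusion row and not with the post-infusion row. The SAP does not say which row it enters.

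**The case against.** The strongest reply is the BLQ rule. A reader might infer that 6 of 20 subjects off drug make the Week 24 mean 30% too low (14/20 = 0.70). That requires near-zero values to be counted, and SAP 11 excludes them. Working step 4 reaches a similar figure only with a long assumed half-life and a very low LLOQ. The objection stands.

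Second, the two distortions need different readings of the sampling instructions. A misfilled Week 21 cell requires that no nominal sample exists; pooling of off-drug samples requires that one does. They cannot both occur for the same subject if one reading is applied. That also stands, and the effects should not be added. But neither reading gives a clean table.

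Third, there are safeguards: the listing shows actual and planned times, and SAP 8.4 also summarises End-of-Pegloticase and ET visits separately. These help a careful reader. The separate display comes in addition to the windowed visit, so it does not remove the sample from Week 21, and no PK table separates on-drug from off-drug values.

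Fourth, PK is exploratory (Protocol 8, SAP 3.3) and summarised only descriptively. This limits the importance and is accepted.

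**Conclusion.** The point holds in a limited form. Both concentration summaries lack a dosing-status restriction that the SAP applies elsewhere, the documents contradict themselves on PK sampling after infusions stop, and the ADA split names no time point.

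The size cannot be fixed from public text. One 14-day sample in the Week 21 cell lowers that mean by about 2% to 3% at an assumed half-life of 7 to 14 days. Pooling recent stoppers lowers a mean by 2.5% to 5% for one such subject among 15 at half-lives of 7 to 21 days. It lowers it more if several stop late and remain measurable.

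A reader might also infer that the ADA effect on exposure is overstated at Week 24 and understated mid-study. The documents do not support a fixed direction. Long-stopped ADA-positive subjects drop out as BLQ and do not lower the mean. The same rule drops on-drug BLQ values caused by fast clearance, which would hide an ADA effect. Mid-study cells are not empty of stoppers either, since End-of-Pegloticase samples map into Weeks 14 and 21. What can be said is that dosing status and ADA status are confounded in this table.

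The primary endpoint is unaffected.

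**What to change.** 1. **SAP 11:** restrict the by-timepoint table and the ADA split to on-treatment samples, using the SAP 10.3 definition plus a limit on time since the last infusion of one dosing interval and the visit window (14 + 3 = 17 days). Summarise or list later samples separately.
2. **SAP 11, ADA split:** base it on pre-infusion samples and count the End-of-Pegloticase sample as a trough. This reduces, but does not remove, the selection of subjects who continue dosing.
3. **SAP Table 5:** do not map End-of-Pegloticase or ET PK samples to Week 21; keep them in the separate row that SAP 8.4 already provides. The 17-day limit alone would not catch a 14-day sample in that cell.
4. **Protocol and SAP:** reconcile Protocol 9.3.3.1.1 with footnote 16 of 2.1, Protocol 9.1, 9.5.7.3 and 9.5.7.4, and SAP 4.1 on whether PK is drawn after infusions stop.

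The cost is SAP wording, a filter on infusion dates already recorded, and a short protocol clarification. The downside is fewer subjects in the later PK cells.

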Inherent in organ transplantation is the need for immunosuppression to maintain the viability of the transplant, and prevent rejection. There are no formal clinical trials of uricases, including pegloticase, in kidney transplant recipients with gout, although pegloticase has been used successfully in a small number of transplant recipients. Hershfield et al. (2014) reported a trial of pegloticase administered as 8 mg intravenously (IV) every three weeks for up to 5 infusions to 30 patients, including 7 kidney transplant recipients, with refractory gout who were receiving immunosuppression with various combinations of mycophenolate mofetil, cyclosporine, tacrolimus, and azathioprine (AZA). Five of the 7 transplant recipients responded well to pegloticase, and only 1 of 7 developed antibodies to pegloticase, compared to 9 of

20 pegloticase-naïve non-transplant recipients who were not on immunosuppressives. Of the two transplant recipients who did not respond well to pegloticase, one discontinued at the time of the second infusion with an unrelated SAE (duodenal ulcer which caused loss of the pancreatic graft), and the other discontinued after the third infusion with an unrelated SAE (myocardial infarction); the subject with the myocardial infarction was also the one transplant recipient who developed anti-pegloticase antibodies.

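### The Kaplan-Meier time-to-positive antibody analysis is not restricted to subjects negative at baseline, so it can mix pre-existing with newly formed antibody

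*SAP*

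**What the plan says.** SAP section 11 treats the two antibodies differently and then plans one time-to-event analysis for both.

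- **Anti-PEG table.** It starts from "Using the ITT Population for anti-PEG IgG antibodies, the number and percentage of subjects with ADA positive at baseline, ADA negative at baseline". It has a combined row, "ADA positive at post-baseline but negative at baseline or with increase in titer from baseline", and also shows the two components separately: "ADA positive at post-baseline but negative at baseline, subjects with increase in titer from baseline who were ADA positive at baseline". The remainder is "ADA negative or subjects with no increase in titer from baseline will be summarized by scheduled timepoint".
- **Anti-uricase table.** It is shorter: "the number and percentage of subjects with ADA positive at baseline and post-baseline will be summarized by scheduled timepoint".
- **Time to event.** Both antibodies then get "Kaplan-Meier estimates of the time to positive anti-PEG, and positive anti-uricase with 25th percentile, median, 75th percentile, and 95% CI", with a curve. The section gives no at-risk set, time origin, censoring rule or handling of baseline-positive subjects.

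SAP 6.1 and SAP 14 assign antibody analysis to the ITT population, defined as all subjects with at least one dose. SAP section 11 schedules antibody samples before the Day 1 infusion, at Weeks 2, 6, 14 and 22, at the End-of-Infusions visit if there is one, at Week 24 or early termination, and at the 3-month follow-up. Protocol 9.6.6 promises only incidence and titers, so it does not fill the gap.

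**The concern.** The antibody question in this trial is about formation. Protocol 7.2 and 9.2 argue that transplant immunosuppression may stop antibodies to pegloticase from forming, and so preserve effect and reduce infusion reactions. A time-to-positive curve addresses that only if the subjects on it could become positive, that is, if they were negative at the start.

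Baseline positives are not a remote possibility. The anti-PEG table has a row for them. Exclusion criterion 9 removes subjects with prior uricase treatment or concomitant PEG-conjugated drugs, but not those who already carry anti-PEG antibody. The reference list also includes a pegloticase trial whose title names pre-existing as well as induced anti-PEG antibody.

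If such subjects stay in the curve, it starts too high and its lower percentiles come too early. With a single arm, there is no control curve to offset this.

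**Working it through.** The documents give no figure for this analysis, so there is nothing to reproduce. The check has two parts.

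**1. Follow one subject through both displays.** Take a subject who is anti-PEG positive on Day 1 before dosing, with the same titer at Week 2.

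- In the anti-PEG table the subject is positive at baseline and later falls in the no-increase row. The newly-positive and boosted rows do not count this subject.
- On the curve the subject is in the ITT population and is positive. The event falls at time 0 if the Day 1 sample counts, or at Week 2 (target Day 15) if only post-baseline samples count.

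The table therefore records no new antibody while the curve records an early event. A programmer who silently dropped this subject would also be within the text, and would get a different curve.

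For anti-uricase the table gives positives at baseline and positives afterwards. It does not link the two within a subject, so the newly positive count cannot be read from it unless nobody is positive at baseline.

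**2. Size, by illustration.** Inputs:

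- N = 20 (Protocol 9.6.9).
- b = number positive at baseline. Not in the documents; assumed 0, 2 or 5.
- r = proportion of baseline-negative subjects who become positive. Assumed 1/7, because Protocol 7.1.2 reports of cited kidney transplant recipients that "only 1 of 7 developed antibodies to pegloticase". As a high alternative, 9/20, from the non-immunosuppressed comparison in the same section.
- No censoring, no rounding to whole subjects, and baseline-positive subjects assumed to remain positive at Week 2.

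Formulas:

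- All dosed subjects on the curve: [b + r(20 − b)] / 20
- Baseline-negative subjects only: r
- Difference: (1 − r) × b/20

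| r | b | All dosed on curve | Baseline-negative only | Difference |
|---|---|---|---|---|
| 1/7 | 0 | (0 + 2.86)/20 = 14.3% | 14.3% | 0 |
| 1/7 | 2 | (2 + 2.57)/20 = 22.9% | 14.3% | 8.6 points |
| 1/7 | 5 | (5 + 2.14)/20 = 35.7% | 14.3% | 21.4 points |
| 9/20 | 0 | (0 + 9)/20 = 45.0% | 45.0% | 0 |
| 9/20 | 2 | (2 + 8.1)/20 = 50.5% | 45.0% | 5.5 points |
| 9/20 | 5 | (5 + 6.75)/20 = 58.8% | 45.0% | 13.8 points |

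The 25th percentile is also exposed. With b = 6 and no induced antibody at all, the proportion still negative drops to 14/20 = 70% at time 0 or Week 2, so the 25th percentile falls there whatever pegloticase does. With b = 5 it drops to exactly 75%, and the reported percentile depends on the software's convention.

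**The case against.** The strongest reply is that the SAP is silent; it does not direct anyone to count baseline positives as events. Time to positive can reasonably be taken to apply only to subjects not yet positive. The anti-PEG table beside the curve gives the baseline-positive, newly positive and boosted counts, and SAP 8.1 puts relevant subject data in listings. The output is exploratory and descriptive, and Protocol 9.6.5 plans no formal efficacy testing.

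Much of that stands. No sentence orders the inclusive reading. It follows from pairing an unqualified event with a population of all dosed subjects, and the defect is that two compliant programs can produce different curves. For anti-PEG, the table lets a careful reader detect the mixing. For anti-uricase it does not. Exclusion 9 makes prior uricase exposure unlikely, but the SAP still expects a baseline-positive count.

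Three stronger readings are tempting, and the documents do not support them:

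- **That the curve counts titer noise.** The Kaplan-Meier event is positivity. A rise in titer appears only in the anti-PEG table and is not said to feed the curve. The table gives no threshold for an increase, but that is a minor clarification to be settled from assay validation data, which are not in these documents.
- **That pre-existing anti-PEG antibody will generally be reported as induced.** The table keeps pre-existing, new and boosted antibody apart, and the SAP never labels the curve as induced antibody.
- **That a planned comparison with the cited 1 of 7 is spoiled.** No such comparison is planned. That trial dosed every three weeks for up to 5 infusions, and its proportion corresponds to the newly-positive row. The 1/7 serves here only as an illustrative rate.

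**Conclusion.** The concern holds for the two Kaplan-Meier analyses and for the anti-uricase summary. The plan does not restrict time to positive to subjects who could become positive. On its literal reading, the curve contradicts the no-increase row of the anti-PEG table and blurs the question of antibody formation.

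The size cannot be fixed from the documents because the baseline-positive count is unknown. The percentages are illustrations under the assumptions listed, not predictions, and the bias vanishes if nobody is positive at baseline. At 1/7 induction the overstatement is about 9 points with 2 baseline-positive subjects and about 21 points with 5. A higher induction rate shrinks it.

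This is a cheap improvement worth making before the antibody data are analysed. It bears on no primary or secondary endpoint, stopping rule or sample size.

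**What to change.** In SAP section 11:

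1. Restrict both Kaplan-Meier analyses, anti-PEG and anti-uricase, to ITT subjects negative for that antibody at baseline. Define the event as the first positive post-baseline sample, with time measured from the first infusion and censoring at the last antibody sample.
2. Report baseline-positive subjects separately for each antibody.
3. Add to the anti-uricase table the row for subjects negative at baseline and positive afterwards, matching anti-PEG.
4. As a minor clarification to the anti-PEG table, state what counts as an increase in titer, taken from the assay validation.

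The cost is a few sentences and a filter on samples already scheduled. The curve loses the baseline-positive subjects from its denominator, for example 15 instead of 20 if 5 are positive, so its intervals will be somewhat wider. If the true rate is near 1/7, the 25th percentile and median will probably not be reached, and the SAP should say that they will then be reported as not reached.
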